#### 5.2 Statistical Analysis

Analyses will be performed using comparisons within patients of same baseline penile stretch length and between groupings of varying lengths. Comparison of penile length between traction and no traction will be made, as well as reviewing historical records to increase statistical power. Comparison of length from baseline to post-traction for individual participants will also be reviewed.

The data will also be analyzed in three ways: 1- with all patients included, regardless of their compliance to utilize the device for the recommended treatment time, 2- with patients excluded if they failed to achieve 90% compliance with the recommended duration of treatment, 3- with patients excluded if they failed to achieve 75% compliance with the recommended duration of treatment. Factors which will also be included to determine compliance will include frequency and duration of use and whether or not the device was used correctly (black rods buried, amount of time white line showing).

Comparisons will also be made on other subjective and objective variables obtained including number of adverse events, complications, subjective responses to questionnaires, or other information. All data will be normalized by baseline stretched penile length.

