## Study Summary

Title	Penile Length Restoration in Men with Diabetes Mellitus, Type II
IRB Protocol Number	18-006696
Methodology	Controlled randomized study
Overall Study Duration	3 years
Subject Participation Duration	6 months
Objectives	Evaluate the efficacy of the RestoreX penile traction device in restoring length loss secondary to diabetes mellitus
Number of Subjects	120
Diagnosis and Main Inclusion Criteria	Men with diabetes mellitus, type II
Study Device	RestoreX®, penile traction therapy
Duration of Exposure	Subjects in Groups 1-3 will use device for 3 months for 30 minutes, twice daily. Subjects in Group 4 will be control and will not use the device.  After the randomized period, subjects using the device will switch to not using the device (Group 1), using the device once weekly x 30 minutes (Group 2), or continuing to use the device twice daily x 3 months (Group 3).
Reference therapy	The use of the device will be compared against a control group using no traction therapy. Individuals will also be compared to themselves to evaluate changes from baseline.
Statistical Methodology	Stratification of subjects prior to randomization to assure an equal representation based on baseline penile length. Statistical comparisons will be made comparing total penile length prior to and following therapy. Comparisons of subjective questionnaire responses will also be made between groups and at the various time points captured.

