### 3.4 Consent and Enrollment

Patients wishing to enroll in the study will be given the opportunity to meet with the study coordinator to further review study details and formal consent.

Patients that would like additional time to consider their participation will be given other opportunities to meet with the study coordinator if desired. If the patient expresses interest in participating at any of these times, a formal consent will be reviewed (see **Attachment – Consent Form**).

At enrollment, all participants will be assigned a study identifier, with a master list maintained in a password protected database (Mayo server – RAVE database) linking the patient to the identifier. A total of 30 patients will be enrolled into each arm of the study for a total of 120 patients enrolled overall. It is estimated that up to 360 patients will need to be screened to enroll the 120 patients.

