### **3.6 Randomization Protocol**

Following enrollment and completion of the initial length assessment, patients will be categorized into the appropriate strata based on their baseline stretched penile length; strata categorized as <10 cm, 10cm-13cm, 13.1cm-16cm, >16cm stretched length. Each stratum will have a separate randomization table provided such that one of three possible outcomes will occur no less frequently than every other case. This is done to better account for baseline variables that may impact outcomes and to assist with matching groupings appropriately.

The explanation of which grouping the patient is assigned will then be reviewed, and if the patient subject is assigned to the treatment group, a RestoreX® device will be provided.

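### Section 5.2 lists several length comparisons but no single treatment estimate adjusted for the randomization strata and continuous baseline length

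*Combined protocol and SAP*

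**What the plan says.** Section 3.6 stratifies the randomization by baseline stretched length, with "strata categorized as <10 cm, 10cm-13cm, 13.1cm-16cm, >16cm stretched length", and adds that "Each stratum will have a separate randomization table provided". Section 3.4 fixes the size: "A total of 30 patients will be enrolled into each arm of the study for a total of 120 patients enrolled overall". Section 2.1 poses one question, length after traction compared with untreated controls.

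Section 5.2 contains the whole length analysis. It opens with "Analyses will be performed using comparisons within patients of same baseline penile stretch length and between groupings of varying lengths". It continues with "Comparison of penile length between traction and no traction will be made", to be supported by historical records, and then a baseline to post-traction comparison for individual men. It ends with "All data will be normalized by baseline stretched penile length". The Study Summary adds "Statistical comparisons will be made comparing total penile length prior to and following therapy".

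None of these is labelled primary. No model, covariate, pooling rule, significance level or contrast among the four groups is given, and normalization is not defined.

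**The concern.** A trial that stratifies its randomization on a factor because it may affect outcome would normally carry that factor into one overall estimate of effect. Section 5.2 does not say that this will be done. An analyst could follow its text and report up to four band-specific answers, a raw overall difference, a change from baseline, or a normalized value. These can disagree, and nothing says which one answers Section 2.1.

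Two things are at stake. The first is precision: separate band results are weak, and an overall comparison that does not use baseline well has a wider interval than it needs. The second is the freedom to choose among results after the data are seen.

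**Working it through.** **Inputs from the documents.** Four groups of 30, 120 in all (Section 3.4; 4 × 30 = 120 agrees). Four length bands (Section 3.6). Groups 1 to 3 share one regimen up to month 3 (Study Summary and Section 3.5), so pooled traction versus control at that visit is 90 v 30.

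**Assumptions.** The documents give no significance level, power, effect size, SD, dropout rate or expected band shares. I take two-sided 5%, 80% power, no dropout, equal allocation within bands, and results in SD units. The plan has no power calculation to reproduce.

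**Cell size.** With equal bands, 30 / 4 = 7.5 men per arm per band, so a band holds 22.5 traction and 7.5 control men at month 3.

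**Standard errors**, SE = SD × √(1/n₁ + 1/n₂), with detectable differences and power from the non-central t:

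| Contrast | SE (SD) | Detectable difference (SD) | Power at 0.60 SD |
|---|---|---|---|
| All men, 90 v 30 | √(1/90 + 1/30) = 0.211 | 0.60 | 81% |
| Band with 25% of men, 22.5 v 7.5 | √(1/22.5 + 1/7.5) = 0.422 | 1.22 | 28% |
| Band with 10% of men, 9 v 3 | √(1/9 + 1/3) = 0.667 | 2.07 | 13% |

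A quarter-size band has 0.422 / 0.211 = 2 times the SE, hence a quarter of the information. For one traction group against control the same ratio holds: 0.516 (7.5 v 7.5) against 0.258 (30 v 30).

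**False positives if bands are tested separately.** 1 − 0.95⁴ = 0.185.

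**What pooling does.** A band with share s has variance (1/90 + 1/30)/s = 0.0444/s, so its inverse-variance weight is 22.5s. The shares sum to 1, so the weights sum to 22.5 and the pooled SE is √(1/22.5) = 0.211, whatever the shares. The loss in the table arises only if the bands are left separate.

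**What baseline adjustment adds.** With equal variances at both visits and baseline to follow-up correlation r, the SE of the adjusted difference is multiplied by √(1 − r²) relative to raw follow-up length, and by √((1 + r)/2) relative to a change score:

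| Assumed r | v raw follow-up | v change score |
|---|---|---|
| 0.7 | 0.71 | 0.92 |
| 0.8 | 0.60 | 0.95 |
| 0.9 | 0.44 | 0.97 |

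Against a change score the SE is therefore 3 to 8% smaller.

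**The case against.** A reader might infer that the plan makes separate band tests its lead analysis in place of an overall one, and so wastes most of the precision of a 120-man trial. The documents do not support that, for four reasons.

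- Section 5.2 calls nothing primary. The opening sentence comes first, but order is not rank.
- The next sentence plans an overall traction versus no-traction comparison, which is not confined to bands.
- The opening sentence speaks of comparisons among men of the same baseline length. It mentions neither tests nor separate reporting, and could describe a stratified analysis whose band results are combined. That analysis loses essentially nothing.
- Baseline is not ignored. The plan compares men with their own baseline and normalizes by baseline length. The large gains (0.71 to 0.44) are measured against an analysis that uses no baseline at all. Against a change score the gain is modest.

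The figure of 7.5 men per arm per band also depends on equal bands, which Section 3.6 does not claim.

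All of this stands, and it limits the size of the point without removing the gap. No pooling step is written, and comparing groupings of different lengths treats the bands as units in their own right. Normalization could mean division, percentage change or subtraction, none of which is covariate adjustment. As worded it applies to all data, so it also reaches questionnaire scores and adverse-event counts, for which dividing by penile length has no clear meaning.

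**Conclusion.** The point holds as a gap in specification with an almost free improvement. Section 5.2 gives no single estimate adjusted for the strata and for continuous baseline length, although both are available for every randomized man.

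The size depends on how the text is carried out. If bands are reported separately, a quarter-size band has twice the SE of the full contrast and four 5% tests have an 18.5% chance of at least one false positive. If bands are pooled, that loss is nil. Baseline adjustment then reduces the SE by 3 to 8% against a change score, and by 29 to 56% against raw follow-up length.

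The band shares, the correlations of 0.7 to 0.9 and the 5% level are assumptions. The 90 v 30 contrast has a common regimen only to month 3. The change should be made, but its absence would not invalidate the trial.

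**What to change.** Replace the opening sentence of Section 5.2, and the normalization sentence as it applies to length, with:

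> Stretched length at follow-up will be compared between randomized groups in one linear model with group, continuous baseline length and randomization stratum. The result is the adjusted difference with 95% CI: Groups 1-3 combined v Group 4 at month 3, and each of Groups 1-3 v Group 4 at month 6. Stratum-specific estimates are descriptive only.

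Both sentences must change. If the normalization sentence stayed, length would be both normalized by baseline and regressed on it. The contrasts and visits need naming because, with four groups whose regimens diverge after month 3, a single adjusted difference is otherwise undefined.

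Analyse IIEF-15 in the same form with its own baseline score, and do not normalize it by penile length.

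The cost is wording only. Length and IIEF-15 are already scheduled at baseline, month 3 and month 6 (Section 4.5). Stratum-by-stratum p-values are given up.

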### 3.5 Study Schema

All patients will have been previously seen at Mayo Clinic for a condition of DM. Following enrollment, key factors relating to their underlying condition will be abstracted from the chart by a study coordinator, including age, duration of disease (if known), number of DM medications, use of insulin, most recent fasting glucose and HbA1c, creatinine, and testosterone, HOMA1-IR, HOMA2-IR, and BMI. If any of these variables are not available, no additional attempts will be made to retrieve the information.

At the initial appointment, patients will also undergo a penile length assessment by a urology provider and Men's Health Nurse and receive questionnaires (IIEF-15 and disease specific history)

Once consent and study assessments are completed, the patients will be randomized into one of four groups:

1. PTT for 30 min 2x/day x 3 months, followed by no treatment x 3 months
2. PTT for 30 min 2x/day x 3 months, followed by once weekly (30 minutes) x 3 months
3. PTT for 30 min 2x/day x 6 months
4. Control (no treatment)

Patients in the treatment arm will record a daily journal of their usage of the device. Patients will then begin using the device as instructed for the times appropriate to their group.

After 3 months of using the device (+1.5 months permitted), patients will return for subsequent assessments (see below) and a follow-up questionnaire. At this time, patients will be encouraged to report any adverse events. They will also be requested to bring their device back to the clinic to review proper usage and any questions on the device. After completion of the subsequent assessments, patients will begin the second phase of the trial.

After 6 months (+ 1.5 months permitted) patients will return to the clinic to undergo final assessments, which are identical to the 3-month assessments.

Since participants are being asked to travel to Mayo Clinic for subsequent assessments, we will provide a remuneration amount of up to \$600. The purpose is to assist participants in their travel to and from Mayo Clinic. Those that provide consent will be provided \$100 after their baseline assessment. After their second and third visits (3 and 6-months, respectively), they will receive \$250 for a possible total of \$600.

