#### 4.4 Assessment of Length

Penile length measurements will be obtained by a member of the clinical team using a measurement from the pubic symphysis to the corona of the glans penis. Measurements will be obtained at baseline and at the 3 and 6 month follow-ups.

See **Attachments – Device Usage Diary, Disease Specific History, IIEF-15, Questionnaire 3 Month and 6 Month**

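### Section 5.2 compares length groupings without tying them to controls; if change is compared that way, regression to the mean alone would make shorter men seem to gain

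*Combined protocol and SAP*

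**What the plan says.** Section 5.2 opens with "Analyses will be performed using comparisons within patients of same baseline penile stretch length and between groupings of varying lengths". It does not define these groupings, name the outcome compared, or say whether arms are pooled or contrasted. Its next sentence plans a comparison of traction with no traction, helped by historical records. It then adds "Comparison of length from baseline to post-traction for individual participants will also be reviewed" and ends with "All data will be normalized by baseline stretched penile length".

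Section 3.6 gives the only length groupings in the document: "patients will be categorized into the appropriate strata based on their baseline stretched penile length", with "strata categorized as <10 cm, 10cm-13cm, 13.1cm-16cm, >16cm stretched length".

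On the number of readings, Section 4.4 says "Measurements will be obtained at baseline and at the 3 and 6 month follow-ups", so there is one baseline occasion. Section 3.5 says "patients will also undergo a penile length assessment by a urology provider and Men's Health Nurse", but does not say whether this yields two readings or how they would be combined. The Study Summary describes the outcome as "Statistical comparisons will be made comparing total penile length prior to and following therapy".

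No baseline-adjusted model, treatment-by-length interaction or separate reading for classification is stated.

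**The concern.** One baseline reading does three jobs: it sorts men into length groups, it is the starting point for change, and it is the divisor for normalised data. Any reading contains some error. Men placed below 10 cm are there partly because they were read low that day, so their next reading tends to rise. Men placed above 16 cm tend to fall. A comparison of change between length groups then mixes this artefact with any device effect.

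At stake is a subgroup statement such as greater gain in shorter men, which would suit a device meant to restore length and could arise with no device effect. Dividing by baseline does not remove the artefact, because the divisor is the same error-prone reading.

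**Working it through.** **The plan's figures.** Four arms of 30 give 4 x 30 = 120, as Section 3.4 states. The plan gives no mean, SD, reading error, effect size or power for length, so there is no planned figure to reproduce for this point.

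**Inputs.** From Section 3.6: the cut points (10, 13/13.1 and 16 cm, with 13.05 used for the middle cut). From Section 3.4: N = 120. Assumed: mean 12 cm; between-man SD 2 cm; reading SD 0.3, 0.5 or 1.0 cm; normal distributions; errors independent between visits; no device effect.

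**Formula.** Write the reading as true length plus error, with reliability R = (between-man variance) / (between-man variance + error variance). With no effect, the expected change in a stratum is (1 - R) x (overall mean - mean baseline reading in that stratum). The stratum means are those of a truncated normal distribution.

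**Worked case, reading SD 0.5 cm.** R = 4 / (4 + 0.25) = 0.941, so 1 - R = 0.0588.

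| Stratum | Expected men of 120 | Mean baseline reading (cm) | Expected null change (cm) |
|---|---|---|---|
| <10 | 20 | 8.905 | 0.0588 x 3.095 = +0.182 |
| 10-13 | 63 | 11.605 | 0.0588 x 0.395 = +0.023 |
| 13.1-16 | 33-34 | 14.140 | 0.0588 x (-2.140) = -0.126 |
| >16 | 3 | 16.784 | 0.0588 x (-4.784) = -0.281 |

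False differences: 10-13 v 13.1-16 cm, 0.023 + 0.126 = 0.15 cm; <10 v 13.1-16 cm, 0.182 + 0.126 = 0.31 cm; <10 v >16 cm, 0.182 + 0.281 = 0.46 cm.

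**All three reading errors.** 1 - R is 0.09/4.09 = 0.022, 0.25/4.25 = 0.059 and 1/5 = 0.20.

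| Contrast | Reading SD 0.3 | 0.5 | 1.0 |
|---|---|---|---|
| 10-13 v 13.1-16 cm | 0.06 | 0.15 | 0.52 |
| <10 v 13.1-16 cm | 0.11 | 0.31 | 1.08 |
| <10 v >16 cm | 0.17 | 0.46 | 1.62 |

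The >16 cm group holds about 3-4 of 120 men throughout.

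**Sensitivity.** Over means of 11-14 cm and between-man SDs of 1.5-2.5 cm, with the same reading SDs, the <10 v >16 cm contrast runs from 0.12 to 2.36 cm. The upper end (mean 11, SD 1.5, reading SD 1.0) expects about 0.3 men above 16 cm, so that contrast would usually not exist in this trial.

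**Percentage of baseline.** In simulations with no effect (mean 11.5-13.5 cm, observed SD 2.0-2.5 cm, reliability 0.95 to 0.70), the apparent change was +1.6% to +16.6% below 10 cm and -1.0% to -9.7% above 16 cm.

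**False positives at N = 120.** These come from 4,000 simulated null trials per reliability, with 90 traction and 30 control men, mean 12.5 cm, observed SD 2.5 cm and an assumed two-sided 0.05 level. Analysis of variance of change across strata was significant in 23%, 46%, 79% and 94% of trials at reliability 0.95, 0.9, 0.8 and 0.7. The treatment-by-baseline interaction was significant in 4.6%-5.0%, and the baseline-adjusted arm contrast in 4.5%-5.3%.

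**Checks.** With perfect reliability the artefact is zero. If men are grouped on a separate reading, mean change in every stratum is within 0.01 cm of zero. Mean change in cm over all men is not shifted.

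**The case against.** The opening sentence of Section 5.2 does not state a faulty analysis. It mentions neither change nor pooling of arms. The next sentence compares traction with no traction, the primary objective in Section 2.1 is framed against untreated controls, and Section 3.6 randomises within the length strata. The sentence may therefore mean traction v control within and across strata, where the artefact cancels. The link between its groupings and the four strata is an inference, and Section 3.6 also uses the word grouping for the assigned arm. None of the seven secondary objectives asks whether the effect depends on baseline length. Averaging two baseline readings would shrink the artefact, and the largest figures depend on a nearly empty cell.

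Most of this stands. A reader might infer that the plan commits to comparing raw change between length groups, or that its main comparison is biased. The documents support neither: the sentence is unspecified, and controls in the same stratum regress by the same expected amount as treated men. What remains is that the wording permits the invalid analysis as readily as the valid one, with within-person change and division by baseline planned alongside. Averaging readings would reduce the artefact, not abolish it.

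**Conclusion.** The point holds in conditional form. If change is compared between baseline-length groups without their concurrent controls, shorter men would appear to gain and longer men to lose with no device effect. The direction needs only some reading error. The size rests wholly on assumed values. For the two strata that hold about 97 of 120 men (at reading SD 0.5 cm), it is modest at small reading errors (0.06 or 0.15 cm) and reaches about half a centimetre at a reading SD of 1.0 cm. The contrasts above 1 cm need that largest reading error and one of the outer groups, and should not be read as the likely error. The randomised traction v control comparison is unaffected, so this is a specification gap in a subgroup analysis that should be closed, not a flaw in the primary comparison.

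**What to change.** Replace the opening sentence of Section 5.2 with a model of follow-up length on treatment and baseline length as a continuous covariate, using concurrent controls. Examine any dependence on baseline length only through the treatment-by-baseline interaction, reported as traction minus control at stated baseline lengths, or as traction minus control within each length range. Label it exploratory. State that change, in cm or as a percentage, will not be compared between length groups without the controls of each group.

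The cost is wording only, as the data are already collected. The drawback is precision. With 30 controls among 120 men, and assuming equal allocation within strata, the worked case leaves about 20/4 = 5 controls below 10 cm and 3/4, or fewer than one, above 16 cm. The interaction will be imprecise, and a within-range estimate at the top may not be possible.

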## 2 Study Objectives

### 2.1 Primary Objective

1. The primary objective is to assess penile length pre and post completion of RestoreX® traction therapy compared to control groups (no treatment) of DM subjects.

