### 2.2 Secondary Objectives

1. Compare patient compliance with traction device.
2. Compare patient reported satisfaction with use of traction device.
3. Evaluate any adverse events (AEs) with use of RestoreX® for penile lengthening.
4. Compare the rate of Peyronie's disease development among groups
5. Compare patient satisfaction scores including satisfaction with overall penile length.
6. Evaluate and compare patient erectile function among groups
7. Review associations between DM factors and standardized questionnaires and outcomes

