## 4 Study Procedures

### 4.1 Baseline Assessments

- Participant consented
- Abstracted from chart
  - Age
  - Duration of DM
  - DM medications including use of insulin
  - Fasting glucose, HbA1c, HOMA1-IR, HOMA2-IR, creatinine, testosterone
  - BMI
- Objective assessments
  - Penile length – pubic symphysis to glanular corona
- Subjective questionnaires
  - Disease specific history
  - IIEF-15
- Device usage diary provided for treatment group

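### Section 5.2 uses undefined historical records to raise power and does not reserve the primary traction v no-traction comparison for randomized men

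*Combined protocol and SAP*

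**What the plan says.** The analysis of length is set out in section 5.2: "Comparison of penile length between traction and no traction will be made", and the same sentence continues "as well as reviewing historical records to increase statistical power". This is the only mention of historical records in the plan. Their source, period, eligibility, method of length measurement and weighting are not given.

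The comparison serves the primary objective in section 2.1, which is to "assess penile length pre and post completion of RestoreX® traction therapy compared to control groups (no treatment) of DM subjects". Section 3.5 randomizes men to four groups, and Group 4 is the only untreated one. On size, section 3.4 says: "A total of 30 patients will be enrolled into each arm of the study for a total of 120 patients enrolled overall".

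The plan also collects chart data on enrolled men. Under section 3.5, "key factors relating to their underlying condition will be abstracted from the chart by a study coordinator". The laboratory items in section 4.1 are "Fasting glucose, HbA1c, HOMA1-IR, HOMA2-IR, creatinine, testosterone", listed with age, duration of diabetes, medications and BMI. Penile length is not among the items taken from the chart. Section 2.2 includes a secondary objective that could use these data: "Review associations between DM factors and standardized questionnaires and outcomes". No section links them to the length comparison in section 5.2.

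**The concern.** Randomization protects the primary comparison only while the men compared are the randomized ones. The clause on historical records sits in the sentence that defines that comparison, and its stated purpose is power. Two analysts could follow section 5.2 faithfully and produce different primary results, one from 120 randomized men and one from a mixture.

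If non-randomized men were added, nothing in the plan would support treating them as exchangeable with the randomized men. Trial participants must pass the exclusions in section 3.1.2, and their length is measured by the clinical team from pubic symphysis to corona at baseline, 3 and 6 months (section 4.4). No such conditions are placed on the historical records. Which records to use, and how much weight to give them, could also be settled after the trial results were known, and a reader could not then separate the randomized effect from the rest.

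**Working it through.** **1. What can be reproduced.** The only relevant figure in the plan is the sample size: 4 arms × 30 = 120, which agrees. The plan gives no power, alpha, effect size, SD or dropout, so the power that the records are meant to increase has no stated starting value.

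**2. What the clause could mean.**

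| Use of the records | Non-randomized men in the contrast? | Consequence |
|---|---|---|
| Enrolled men's own charts, as baseline covariates | No | Can raise power without bias |
| Other men's records, to build a prognostic score applied as a covariate to randomized men | No | Can raise power; the contrast stays randomized |
| Other men's records, in a separate descriptive review | No | Primary contrast unaffected |
| Other men added to the comparison | Yes | Biased unless exchangeable on change in length |

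The aim of raising power fits the first, second and fourth rows, so it does not choose among them. The absence of length from the abstracted chart items is weak evidence against the first row, because a covariate need not be a length.

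**3. Illustration for the fourth row only.** Inputs from the plan: 30 men per arm. Inputs assumed here, with no basis in the plan: H records pooled as controls at full weight; their mean change differs from Group 4 by a shift of b SD; no true treatment effect; two-sided alpha 0.05; no dropout; SD of change equal to 1. The contrasts are also chosen here: Groups 1–3 combined at month 3 (nT = 90), because they share one regimen up to then, and a single traction arm at month 6 (nT = 30).

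- Bias = b × H/(30 + H)
- SE = √(1/nT + 1/(30 + H))
- Type I error = P(|Z + bias/SE| > 1.96)

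For H = 90 and b = 0.2, bias = 0.2 × 90/120 = 0.15 SD.

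- Month 3 (90 v 120): SE = √(1/90 + 1/120) = 0.139; bias/SE = 1.076; type I error = 0.189.
- Month 6 (30 v 120): SE = √(1/30 + 1/120) = 0.204; bias/SE = 0.735; type I error = 0.114.

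| H | Shift b (SD) | Type I error, month 3 | Type I error, month 6 |
|---|---|---|---|
| 90 | 0 | 5% | 5% |
| 90 | 0.1 | 8% | 7% |
| 90 | 0.2 | 19% | 11% |
| 90 | 0.3 | 36% | 20% |
| 30 | 0.2 | 9% | 7% |

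All the inflation comes from the bias; the SE is correct under this model.

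**4. The other side of the trade.** Without pooling, SE is √(1/90 + 1/30) = 0.211 at month 3 and √(1/30 + 1/30) = 0.258 at month 6. Mean squared error is SE² + bias². For H = 90 and b = 0.2:

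- Month 3: 0.0194 + 0.0225 = 0.0419 pooled, against 0.0444 randomized only.
- Month 6: 0.0417 + 0.0225 = 0.0642 pooled, against 0.0667 randomized only.

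The break-even shift is √(1/30 − 1/120)/0.75 = 0.158/0.75 = 0.211 SD at both visits, because the treated-arm term cancels. So at 0.2 SD pooling still has the slightly smaller mean squared error, even though its type I error is no longer 5%.

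**The case against.** The tempting stronger reading is that the plan will pool historical men with Group 4 and that its primary result will therefore be biased. The documents do not say this. The verb is reviewing, not pooling, and the grammar allows an activity alongside the comparison rather than a change to its control group. The Study Summary names as comparators a no-traction control group and the men's own baseline, and its statistical row does not mention historical data. Section 5.1 has data recorded on printed forms by the patient or provider, which leaves no evident route for men who were never enrolled. Nor do other men's records have to enter the contrast to raise power, as a prognostic score shows.

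These points make pooling less likely but do not exclude it. Coordinator chart abstraction, which the plan does require, also fits section 5.1 poorly. The primary objective speaks of control groups in the plural although the design has one. No sentence restricts the comparison to randomized men.

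Two further objections stand. The figures above are driven wholly by assumed inputs, so they show a mechanism and do not measure a defect in this plan. And part of the gap is wider than this clause: section 5.2 names no primary time point, arm contrast or test. The present point should be confined to which men enter the comparison.

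**Conclusion.** The point holds as an undefined analysis step attached to the comparison that serves the primary objective. Bias follows only if non-randomized men are added to the comparison and are not exchangeable with the randomized men on change in length. Its size and direction cannot be found from the documents. A reader might infer that the result will be biased, or that 19% is the trial's actual error rate. Neither is supported: the first needs a use of the records that the plan does not state, and the second needs a record count, shift and weight that it does not give. Correcting the clause is a cheap improvement, with medium confidence that it would matter in practice.

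**What to change.** In section 5.2, replace the clause on historical records with:

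> *The primary traction v no-traction comparison uses only randomized participants, with Group 4 as the control. Chart data of enrolled men may be used as baseline covariates. Any analysis that includes non-randomized men is reported separately as exploratory, with source, eligibility, length measurement and weighting fixed before outcome data are reviewed.*

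This leaves the harmless uses open and does not prohibit historical data. The editing cost is one clause replaced by three sentences.

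The statistical cost is lower nominal precision than pooling would give. Against 90 pooled records, the month-3 SE is 0.211 rather than 0.139 SD (95% CI half-width 0.41 v 0.27 SD), and the month-6 SE for one arm v control is 0.258 rather than 0.204 SD (0.51 v 0.40 SD). If the true shift were below about 0.21 SD, a real gain in mean squared error would be forgone, but the plan offers no basis for judging the shift. No stated power is lost, because the plan states none.
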